**Table 6: Summary Benchmarks Preferred Practice Pattern Guidelines for POAG**

Target IOP Achieved	Progression of Damage	Duration of Control (months)	Appropriate Follow-up Interval (months)
Yes	No	<6	6
Yes	No	>6	12
Yes	Yes	NA	1-2
No	Yes	NA	1-2
No	No	NA	3-6

Source: *American Academy of Ophthalmology*

## D. EVALUATION/PERFORMANCE MEASUREMENTS

We have created distal and proximal follow-up protocols to measure public health outcomes during Phases 1, 2, and 3, with the capacity to improve quality of vision and eye health and quality-of-life in real-life settings. Outcomes may vary among our study populations depending on the diagnosis and follow-up recommendations. We have developed the research project within the *RE-AIM Framework*, as described below and focus on integrating into the vision and eye care systems of each of our partners. Westat will assist with to the evaluation process.

D.1.a. Reach: The number of patients from our partners’ primary care offices and health centers who have not seen an ophthalmologist in the past year is estimated to be more than 10,000. We conservatively estimate that 2,500 of these patients will schedule, attend, and participate in Visit 1 in the primary care setting, where we will detect glaucoma and other eye diseases using telemedicine. Based on previous demonstration projects, 2,500 patients is a reasonable and realistic number to recruit. The proportion of patients who are African American,

Caucasian, Hispanic, and Asian at each partner organization is described in the Facilities section. We will report on the demographics of the study sample, defined as the similarity to or differences between participants and eligible people who do not enroll. If differences exist in the demographic variables between our intervention and control group, our intervention may be less generalizable in other patient populations. If differences do not exist, then a stronger case can be made for generalizing the intervention into additional settings.

**D.1.b. Effectiveness/Efficacy:** We will evaluate the impact of our enhanced intervention on our proposed outcomes, including quality-of-life, and economic efficiency. Determining the effectiveness of our intervention is critically important because patients with undetected glaucoma and other eye diseases can suffer lasting visual impairment that can affect their quality-of-life, economic status, morbidity, and ultimately mortality. New strategies are necessary to improve patient access and utilization of eye care. Our study aims to determine if adherence to follow-up recommendations changes as a result of the enhanced intervention. We will determine the effectiveness of the intervention by examining the effect size associated with our intervention and specified outcomes (adherence to follow-up recommendations and vision-related quality-of-life).

**D.1.c. Adoption:** Our letters of support from Advisory Board members and partner institutions demonstrate a strong commitment and willingness to participate in this research study. We are working closely with primary care offices, health centers, universities, governmental agencies, and community organizations. We expect to notice variations in patient behavior based on the number of resources available to them. These varying settings and intervention modalities are critical to the current and potential impact of our intervention. If differences exist among sites, this is evidence of differential adoption.

**D.1.d. Implementation:** At each setting, implementation refers to the intervention agents' fidelity to all elements of the protocol. This includes consistency of delivery as intended and the time and cost of the intervention. Investigators in coordination with Westat and the project manager will determine the extent to which the intervention was delivered. We will assess implementation by reporting on the percentage of process objectives that were achieved, such as: What proportion of patients received the confirming diagnosis enrolled in the study? How many patients followed up with the general ophthalmologists at the initial 6-month, 1-year, 2-year, and 3-year visits. We will also conduct a cost analysis and report costs of all levels of the intervention, including recruiting patients, reading images, confirming diagnoses, randomization, and 3-year follow-up (Table 7).

**D.1.e. Maintenance:** Our research has the advantage of building on existing infrastructure of both the WETD, and currently established community referrals to general ophthalmologists, which will remain in place after the research is completed. The extent to which a program or policy becomes institutionalized at each community partner will be evaluated. This project will allow evaluation data to be captured at all detection and implementation levels. Following the completion of the 5-year study, we will communicate our results to our partners', present data, and discuss strategies that worked to improve patient care. The outcomes of our study will be highly applicable for improving the cost of eye care for newly diagnosed patients with glaucoma and other eye diseases. In anticipating the success of our proposed study, we plan to institutionalize the program in Philadelphia, and monitor long-term outcomes after 6 or more months. Using the *RE-AIM Framework*, we will track intervention data shown in Table 7.

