**C.7. Enhanced Intervention Versus Usual Care Group:**

*Group 1: Enhanced Intervention Group with Patient Navigation and Social Worker:* Patients randomized to Group 1 will be provided a list of eye care providers to choose from for follow-up. Patients can also choose to follow-up with an eye care provider not on our list. In that instance we would require a record release to be signed by the patient for the purpose of having access to their follow-up records throughout the study. Prior to all follow-up visits, patients in the enhanced group who have scheduled an appointment will receive a personal phone call reminding them to attend. These patients will receive any necessary interpretation services and educational materials.

*Group 2: Usual Care:* Patients randomized to Group 2 will be recommended to follow-up for eye care with a local eye care provider. These patients will be provided a list of eye care providers to choose from for follow-up. Patients can also choose to follow-up with an eye care provider not on our list. In that instance we would require a record release to be signed by the patient for the purpose of having access to their follow-up records throughout the study. Group 2 represents a realistic choice currently available for patients. Practice patterns will vary depending on the resources, staff time, and services available within each local eye care providers practice.

**C.7.a. Sample Size Determination:** As shown in Figure 1, we have based our sample-size calculations on the current preliminary CDC-project results as well as telemedicine statistics. We project that 30% of those fundus photographs will be abnormal and that, of those, 40% of patients will likely agree to consent and enroll in the study. These patients will be randomized to either the Enhanced Intervention Group 1 or Usual Care Group 2.

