**Figure 1: Sample Size Determinates for Randomization**

**C.7.b. Randomization Groups:** The biostatistician, will randomize patients who meet the inclusion criteria with a fixed scheme 1:1 allocation ratio to the 2 study groups. Eligible patients will be consented and randomized to either the usual care group or the enhanced intervention group using the method of random permuted blocks.

**C.7.c.** The following two sites have eye care providers and all patients of these sites will receive initial and follow-up care throughout this study within these specific sites. As a result of this situation the following two sites will differ slightly from the other sites in terms of randomization and intervention:

Philadelphia Department of Public Health - Health District #5 (All Patients Usual Care): Patients will not be randomized at this site, they will all be assigned to usual care. Patients will be seen only by the eye care provider at Health District #5 for their follow-up eye care. They will be scheduled for their first appointment within 4 to 6 weeks from the date of Visit 2 and will then be responsible for scheduling the remainder of their follow-up appointments.

PHMC - Mary Howard Health Center (All Patients Intervention): Patients will not be randomized at this site, they will all be assigned to intervention. Patients will be seen by the eye care provider at Mary Howard Health Center. They will be scheduled for their first appointment within 4 to 6 weeks from the date of Visit 2. Prior to all follow-up appointments a patient navigator will call and remind them about the date and time of their next appointment. The navigator will also be available to answer any insurance questions they may have or help to arrange transportation to their appointments.

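### Section D.1.a draws its generalisability conclusion from demographic differences between the two arms, which carry no information on how enrolled patients differ from eligible people who did not enrol

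*Combined protocol and SAP*

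**What the plan says.** Three consecutive sentences in D.1.a matter.

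- The first commits to reporting the demographics of the sample, "defined as the similarity to or differences between participants and eligible people who do not enroll".
- The second gives the unfavourable reading: "If differences exist in the demographic variables between our intervention and control group, our intervention may be less generalizable in other patient populations".
- The third gives the favourable reading: "If differences do not exist, then a stronger case can be made for generalizing the intervention into additional settings".

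On allocation, C.7.b states that the biostatistician "will randomize patients who meet the inclusion criteria with a fixed scheme 1:1 allocation ratio to the 2 study groups", by random permuted blocks. C.7.c makes two exceptions. At one health centre, "Patients will not be randomized at this site, they will all be assigned to usual care". At another, "Patients will not be randomized at this site, they will all be assigned to intervention". The expected number of patients at these sites is not given.

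On selection into the study, D.1.a puts the source pool at more than 10,000 and expects 2,500 at Visit 1. C.4.a gives about 1,250 recruits. C.7.a projects that 30% of photographs will be abnormal and that, "of those, 40% of patients will likely agree to consent and enroll in the study".

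**The concern.** The first sentence asks whether the people studied resemble the people the programme is meant for. The next two answer a different question: whether the two arms resemble each other. That second question concerns internal validity. Two randomised halves of a highly selected group will resemble each other just as closely as two halves of a representative group.

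Replication in other communities is Aim 4, and C.4.b and E.1.a expect generalisable results, so the reading matters. The sponsor's earlier chart review of patients with diabetes (C.3.a) linked older age to better follow-up adherence (odds ratio 1.46, 95% CI 1.18 to 1.80). If enrolment is selective by age, adherence in the trial could differ from adherence in the source population, and an arm comparison would not show it.

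**Working it through.** D.1.a attaches no figure, test or threshold to its interpretation, so there is no stated number to reproduce. The check has four parts.

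**1. Room for selection, on the plan's figures**
- Attending Visit 1: 2,500 / 10,000 = 25% at most (D.1.a), or 1,250 / 10,000 = 12.5% at most (C.4.a). The pool is given as more than 10,000.
- Abnormal images: 2,500 × 0.30 = 750. Enrolled: 750 × 0.40 = 300, which matches the 300 randomised in E.2.d. C.4.a gives 374.
- Abnormal but not enrolled: 1 − 0.40 = 60%.

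**2. What each comparison detects**

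Assumptions (not in the plan): one binary demographic trait present in 50% of 750 eligible people; 300 enrol; the trait changes the odds of enrolling by a factor OR; two-sided z-tests at 0.05; 200,000 runs; everyone enrolled is randomised 1:1.

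Let e1 and e0 be the enrolment probabilities with and without the trait. They solve 0.5·e1 + 0.5·e0 = 300/750 = 0.40 and e1/(1 − e1) = OR × e0/(1 − e0). The trait's prevalence is then 0.5·e1/0.40 among the enrolled and 0.5·(1 − e1)/0.60 among the rest. Both arms share the first value, so the expected arm difference is zero at every OR.

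| OR | Trait, enrolled | Trait, not enrolled | Arms differ (150 v 150) | Enrolled v not differ (300 v 450) |
|---|---|---|---|---|
| 1 | 50.0% | 50.0% | 5.7% | 5.1% |
| 1.5 | 56.1% | 46.0% | 5.4% | 77.4% |
| 2 | 60.3% | 43.1% | 5.2% | 99.6% |
| 3 | 66.0% | 39.3% | 4.9% | about 100% |
| 5 | 72.8% | 34.8% | 5.0% | about 100% |

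With 374 enrolled and 376 not, the arms differ in 4.9 to 5.6% of trials. The enrolment comparison flags 5.3%, 79.8%, 99.8%, about 100% and about 100%.

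**3. Several variables**

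For k independent variables each tested at 0.05, the chance of at least one arm difference is 1 − 0.95^k: 14% for 3, 23% for 5 and 34% for 8. This too is the same whatever the enrolment pattern.

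**4. The two single-arm sites**

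Site sizes and prevalences are assumed; the total is 300, with 50% prevalence elsewhere. The table shows how often the arms differ at 0.05.

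| Patients per site | Prevalence 30% v 70% | Prevalence 10% v 90% |
|---|---|---|
| 5 | 6% | 8% |
| 10 | 8% | 16% |
| 20 | 16% | 48% |
| 30 | 30% | 82% |

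Arm differences can therefore be common, but their cause is how those sites were assigned, not who enrolled.

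**The case against.** The strongest reply is that the right comparison is already promised one sentence earlier, and that the arm wording is probably a drafting slip. The text is hedged narrative in the RE-AIM section and feeds no analysis in section E. D.1.d also reports the proportion of confirmed patients who enrol, and Table 8 counts patients scheduled, attending and cancelling.

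Much of this stands. A reader might infer that the plan ignores non-enrollees. It does not: the report is promised, and only the conclusion is tied to the wrong comparison. A reader might also infer that the stated reading would almost always favour generalising. The documents do not support that, because they set no test or list of variables, and parts 3 and 4 show that arm differences could be fairly frequent.

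The reply does not rescue the two sentences. They are the only ones that link data to a generalisability conclusion, and the promised comparison has no conclusion attached. The Reach row of Table 7 lists patient characteristics from intake forms and the EMR, with no measure for non-enrollees.

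**Conclusion.** The point holds as a fault of interpretation. Balanced arms do not strengthen the case for generalising, and unbalanced arms do not weaken it, because neither says how enrollees differ from the eligible population. This follows from the design and does not depend on the assumed trait prevalence, test level or site sizes, which serve only to illustrate it. It is also unchanged by the disagreement between 2,500 and 1,250 recruits, or between 300 and 374 randomised.

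The consequence is limited to what the trial may claim about wider use. A reader might infer that the adherence comparison is compromised by this wording. It is not: no estimate, test or sample size for Aims 1 to 3 relies on these sentences. The correction is worth making because Aim 4 rests on generalising and the change is cheap.

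**What to change.** Reword the two conditional sentences in D.1.a so that the judgement rests on the comparison already promised, at two steps:

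- **(a) Visit 1 attendees against eligible listed patients who did not attend.** Use the variables the partner lists hold, such as age, race/ethnicity and diabetes. The lists are built from the inclusion criteria (C.5.a), so include sex and insurance only where available.
- **(b) Randomised patients against all Visit 1 patients eligible for randomisation but not randomised, using Visit 1 intake data.** Include those who declined and those with abnormal images who did not return for Visit 2. The second group may be large: E.2.a implies 250 / 0.50 = 500 returning, against 750 abnormal, so about 250 would be missed if only Visit 2 attendees were counted. Show patients from the two C.7.c sites separately, since they enter an arm without randomisation.

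Report both descriptively as standardised differences, and add the measure to the Reach row of Table 7. Keep the arm comparison only as the Aim 2 baseline-balance table (E.2.b). State that demographic similarity does not rule out selection on willingness to attend visits.

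The cost is two reworded sentences and one descriptive table. Non-attendee data may be limited to list variables, and the generalisability statement may become less favourable.

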#### **C.4. Research Design and Methods**

**C.4.a: Project Overview:** The Wills Eye Glaucoma Research Center will conduct a 5-year prospective, randomized controlled trial to evaluate an innovative, community intervention using posterior fundus photographs of the optic nerve and macula to improve access and utilization of eye care to detect, treat, and manage high-risk patients with previously undiagnosed glaucoma, glaucoma suspect, and other eye diseases. L. [name]; [name]; and [name], RD, will lead the research study.

Our diverse targeted, at-risk population includes African Americans, Hispanics, and Asians over age 40; other older adults (aged 65+); individuals over age 40 with a family history of glaucoma and/or with diabetes. Approximately 1250 patients will be recruited from geographically diverse locations across Philadelphia and Chester counties, with the help of our community partners. **Phase 1** will consist of detecting eye disease in 7

primary care offices and 10 FQHC using telemedicine (Visit 1), followed by a comprehensive eye exam by a Wills glaucoma specialist in the same setting to confirm the diagnosis (Visit 2). Based on preliminary data, 30% of patients (approximately 750) will have abnormal optic nerve and/or macula images. The predictive accuracy of the optic nerve images to detect glaucoma and glaucoma suspect as confirmed by the comprehensive eye exam will be evaluated.

**Phase 2** will involve consenting, enrolling, and randomizing 374 patients to either the usual care group (n=187) or the enhanced intervention group (n=187). The enhanced intervention will consist of using patient navigators and a social worker to reduce barriers to follow-up eye care. **Phase 3** will consist of following patients proximally (6 months) and distally (3 years) while they attend appointments with a local, eye care provider (Visits 3-7). Adherence to follow-up recommendations for eye care will be the primary outcome measure. A comprehensive cost study to estimate the intervention costs and cost-effectiveness of detecting eye diseases and vision impairment in a high-risk population will also be conducted. Protocols, materials, outcomes, and results will be disseminated to other communities in order to expand detection of glaucoma, other eye diseases, and visual impairment, and to further refine these approaches to successfully scale the program up to a national level.

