C.8. Patient Navigation Protocol (Appendix I): The use of patient navigators and social workers has proven successful in cancer care programs, showing higher rates of follow-up care, while increasing patient satisfaction and decreasing anxiety. Patient navigation shows promise as the missing link between available services and healthcare delivery to vulnerable populations. By educating and guiding patients, navigators can lessen the disparities among racial/ethnic groups at risk for eye disease. Our study staff, project managers, ocular technicians, and research assistants have been trained to serve as patient navigators. Their responsibilities will include: phoning patients to schedule appointments; confirming appointments by mailings, emails and/or text messaging; arranging transportation through Customized Community Transportation (CCT) and Philadelphia Paratransit Service; and scheduling trained medical interpreters.

Wills Eye ocular technicians will also assist patients in the enhanced intervention group across 17 sites with medication refills and obtaining free medications from pharmaceutical companies. Our patient navigators can identify cultural and language differences and are aware of health literacy issues. We will also provide multiple outreach strategies as additional barriers are identified. Results will be discussed at our weekly research team meetings, quarterly meetings with each partner, and annual meetings with our Advisory Board.

C.8.a. Identifying Barriers to Follow-up Using Social Workers: Research shows that individuals at high risk for glaucoma are not likely to participate in screening programs or ongoing follow-up with an ophthalmologist in an office-based setting. Appendix J describes how innovative approaches to identifying and remediating barriers have been accomplished in our current CDC glaucoma detection program and can be tested, refined, and implemented in this proposed study (Section C.2.a). Educational materials may help non-adherent patients to understand the benefits of taking glaucoma medications regularly.

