**Table 7: Tracking Measures Using *RE-AIM Framework* Approach**

RE-AIM	Evaluation Question	Tracking Measures	Data Source
Adoption	How were community partners and primary care settings engaged in the study?	# of participating community partners and primary care settings (offices, health centers). Primary care offices' satisfaction with participation.	Contact log  On-site observations On-site interviews

Reach	To what extent are high risk target populations being reached?	Patient characteristics (demographics, insurance status, ocular history, ocular risk factors).	Intake form/EMR
Implementation	How was the program implemented?	Patient navigator, cultural competency training conducted. # of staff at each onsite activity. # of patients who follow up with general ophthalmologists. Time taken per patient and for each eye exam. # of confirmatory diagnosis from fundus photos. # of referrals made based on NEI-VFQ.	Planning log  On-site observations  EMR
Efficacy/ effectiveness	Did the intervention work? (Comparison between intervention and control groups)	# of patients from each group adhering per year. Average percentage of visits attended per year. Clinical measures (visual acuity, IOP, VF). Health related quality-of-life (Visits 2 and 8). Satisfaction with eye services at each visit.	EMR  EMR NEI-VFQ Patient satisfaction survey
Maintenance	To what extent has the program been institutionalized?	Willingness of partners and PCPs to continue with telemedicine and community model.	On-site interviews

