**Table 9: Assessment of Adherence to Follow-Up Recommendations**

Recommended Follow-up	Number of visits per year considered adherent to recommendations
1-2 months	At least 6 visits per year with an eye care provider
3-6 months	At least 3 visits per year with an eye care provider
6 months	At least 2 visits per year with an eye care provider
12 months	At least 1 visit per year with an eye care provider

E.2.c. Primary Analysis for Aim 2: The primary outcome of the study is adherence to recommended follow-up in each year as described in section E.1.c. For each of the 3 years of follow-up, we have a dichotomous measure of adherence. We will model this longitudinal dichotomous outcome using Poisson regression within a generalized estimating equation (GEE) framework. Our model will include time (Year 1, 2, and 3), randomization assignment, randomization by treatment interaction, and baseline individual characteristics believed to be associated with adherence to follow-up, including age, diagnosis, vision impairment, and overall vision-related quality-of-life. Within this model, we will test 2 hypotheses.

First, we will compare randomization groups at Year 1 to test whether there are differences in early adherence. Second, we will calculate the average effect of randomization across Years 2 and 3 and test the long-term efficacy of the intervention. In both cases, we will estimate the overall relative risk of adherence along with its associated confidence interval. Each test will be performed with alpha=0.025. The primary analysis will include all patients who were randomized and have some adherence data (see section on missing data below).

E.2.d. Power for the Primary Analysis for Aim 2: Our estimated available sample size is given in Figure 2. We will randomize 300 patients (150 per group). Assuming up to 10% dropout where adherence cannot be calculated due to death or study withdrawal (i.e., final analysis dataset of n=135 per group), we calculate power to detect a 20% improvement in adherence under various assumptions of adherence under Usual Care. We have greater than 80% power to detect these differences using a two-sided chi-square test with alpha=0.025 (Table 10).

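### D.1.c treats any difference among sites as evidence of differential adoption, but patient-level differences among about 17 small sites are practically certain by chance, and Table 7 measures adoption another way

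*Combined protocol and SAP*

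**What the plan says.** D.1.c first sets out an expectation: "We expect to notice variations in patient behavior based on the number of resources available to them". It then says the varied settings and intervention modalities matter for the impact of the intervention, and closes with "If differences exist among sites, this is evidence of differential adoption". It names no outcome beyond patient behaviour, and no test, interval or minimum difference.

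Table 7 handles adoption at the level of the setting. Its Adoption row tracks the number "of participating community partners and primary care settings (offices, health centers") and the primary care offices' satisfaction with taking part, drawn from contact logs, on-site observation and interviews. Patient follow-up with ophthalmologists is in the Implementation row, and adherence is in the Efficacy/effectiveness row.

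C.7.c takes two sites out of randomisation. For Health District #5 it says: "Patients will not be randomized at this site, they will all be assigned to usual care". At the Mary Howard Health Center all patients are assigned to the intervention.

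The models in E.2.c to E.2.f contain no site term, random site effect or test of site heterogeneity.

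**The concern.** Patient-level results differ between sites for reasons unrelated to adoption: sampling error, case mix, local resources and, at two sites, allocation of every patient to one arm. A statement that takes any difference as evidence of differential adoption, with no allowance for these, will be met whether or not adoption differs.

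It also points at a different construct from the one tracked in Table 7. An evaluator following D.1.c would read adoption from patient behaviour; one following Table 7 would read it from participation and office satisfaction. The two could disagree, and the plan does not say which governs. What is at stake is how site differences are interpreted in the RE-AIM evaluation, not the randomised comparison.

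**Working it through.** **Inputs from the plan**

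- Sites: 7 primary care offices plus 10 health centres (C.4.a). C.8 likewise refers to "patients in the enhanced intervention group across 17 sites".
- Randomised patients: E.2.d says "We will randomize 300 patients (150 per group"); C.4.a speaks of "consenting, enrolling, and randomizing 374 patients". The two figures disagree, so both are carried.
- Dropout: "Assuming up to 10% dropout where adherence cannot be calculated due to death or study withdrawal" (E.2.d), leaving 135 per group, or 270.
- Adherence rates: 35% to 60% under usual care and 20 points higher under the intervention (Table 10).
- Visit 1 patients: 1,250 (C.4.a) or 2,500 (D.1.a).

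**Assumptions, not in the plan:** an even spread of patients over sites; the two C.7.c sites counted among the 17; and, for steps 2 and 3, adherence in one year as the patient behaviour in question.

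**Step 1. The plan's own figure.** The plan states no expected gap between sites, so the nearest figure to reproduce is Table 10. The normal-approximation power for two proportions (pooled variance under the null, no continuity correction, n = 135 per group, two-sided alpha 0.025) gives 86.1, 85.7, 86.1, 87.2, 89.1 and 91.6%. Table 10 prints 86, 86, 86, 87, 89 and 92%. The inputs are therefore read correctly.

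**Step 2. Patients per site.** 300/17 = 17.6; 374/17 = 22; 270/17 = 15.9. Restricted to 15 randomising sites: 300/15 = 20 and 374/15 = 24.9. The range is 16 to 25 per site.

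**Step 3. Chance gap with identical sites.** For k sites sharing one true rate p, draw X_i ~ Binomial(n, p) and take max(X_i/n) − min(X_i/n). There were 60,000 runs per scenario.

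| Scenario | k | n per site | Mean gap in points, p = 0.35 to 0.60 |
|---|---|---|---|
| 270 analysed | 17 | 16 | 42 to 44 |
| 300 randomised | 17 | 18 | 40 to 42 |
| 374 randomised | 17 | 22 | 36 to 38 |
| 300, randomising sites only | 15 | 20 | 37 to 38 |
| 374, randomising sites only | 15 | 25 | 33 to 34 |
| 1,250 at Visit 1 | 17 | 74 | 20 to 21 |
| 2,500 at Visit 1 | 17 | 147 | 14 to 15 |

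For 17 sites of 18 patients at p = 0.5, the median gap is 38.9 points (5th to 95th percentile 27.8 to 55.6). No run in any scenario gave equal proportions at all sites. One illustrative uneven split of 300 patients (4 to 40 per site) gave a larger gap, about 55 to 57 points.

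For contrast, a chi-square test of homogeneity on 16 degrees of freedom at the 0.05 level flagged about 4.5 to 4.7% of such null datasets (17 sites of 18). The step from a raw difference to a conclusion is what fails, not the idea of examining sites.

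**Step 4. The non-randomising sites.** Take Table 10's row with 40% under usual care and 60% under the intervention. An all-usual-care site is expected at 40%, an all-intervention site at 60%, and a 1:1 site at (40 + 60)/2 = 50%. The two special sites differ by 20 points, and each differs from a randomising site by 10 points, with adoption the same everywhere. More patients do not remove this.

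**Step 5. The two descriptions of adoption.** D.1.c ties differences among sites to patient behaviour and calls them adoption. Table 7 puts patient follow-up and adherence in other rows and defines adoption by participation and office satisfaction. The two passages do not match.

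**The case against.** The strongest reply is that D.1.c is one narrative sentence in the RE-AIM section, not an analysis rule. The inferential plan is in E.2 and does not use it. Section D.1.e says the tracked intervention data are those in Table 7, so the differences in question could be read as differences in Table 7's setting-level measures, to which no binomial calculation applies. D.1.c itself attributes variation to resources, and the opening of Section D expects outcomes to vary with diagnosis and follow-up recommendations, so confounding is not wholly overlooked.

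Much of this stands. The sentence is descriptive and names no outcome, so the gaps above are conditional illustrations. But it is worded without condition, the only variation the paragraph names is in patients, and nothing in E.2.c to E.2.f qualifies it. If Table 7's measures were meant, the sentence should say so.

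Three stronger readings are tempting and not supported:

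- A reader might take a 40-point chance gap as a property of this trial. It needs about 18 patients at every site, which the plan never states.
- A reader might infer that the Aim 4 dissemination will report some settings as adopters and others not. Section F says its use of RE-AIM will focus on implementation and maintenance, and it lists no site-level adoption claim.
- A reader might infer that the primary comparison is compromised by this sentence. It is not used there.

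**Conclusion.** The point holds as a matter of interpretation. As worded, D.1.c would find differential adoption practically every time, even with identical sites. The expected chance gap is roughly 33 to 44 points if the measure is adherence among randomised patients at 16 to 25 per site, and about 15 to 20 points if it is a proportion among all Visit 1 patients. These sizes rest on an even spread and on a choice of outcome that the plan does not make. The conclusion itself does not: exact equality never occurred, the C.7.c sites differ by the arm effect at any sample size, and the conflict with Table 7 needs no arithmetic. The issue is minor and leaves Aim 2's estimate, alpha and power unchanged.

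**What to change.** Replace the last sentence of D.1.c with wording to this effect: adoption will be assessed only by the Adoption measures in Table 7, namely participating partners and settings and the primary care offices' satisfaction with participation.

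Report site variation in adherence separately and label it descriptive. Use a between-site variance with its confidence interval, from a model adjusted for arm and restricted to the randomising sites. State that no conclusion about adoption is drawn from it. A formal site-by-arm test is not worth adding: with about 10 patients per arm per site (300/15/2) it would be uninformative.

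The cost is one sentence of protocol wording and one extra descriptive analysis of data already being collected. The drawback is that a variance estimated from about 15 small sites will be imprecise, which the interval will show.
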